These preclinical data provide a strong scientific premise for the hypothesis that normalization of extracellular glutamate levels (i.e., restoration of glutamate homeostasis) is a promising pharmacotherapeutic approach for AUD, yet this research area remains unexamined in prospective clinical studies. Because ceftriaxone must be administered intravenously and can result in serious side effects (e.g., *C. Difficile* infection), as well as antibiotic resistance, it is not feasible for testing as an AUD treatment in clinical research. NAC can be administered orally and has a low incidence of side effects making it an ideal lead compound to be evaluated as a potential medication for treating AUD. Although we are not aware of any clinical studies that have prospectively tested NAC for AUD, there is clinical evidence, including data from our laboratory, supporting its utility in treating other substance use disorders linked to disrupted glutamate homeostasis.

The overarching goal of this application is to demonstrate that restoration of glutamate homeostasis with NAC is a viable strategy for treating AUD. This goal will be achieved through the conduct of a rigorous human laboratory study designed to accomplish three specific aims.

The first aim is to demonstrate that maintenance on NAC reduces the pharmacodynamic effects of ALC that contribute to its abuse. A within-subjects study will be conducted in which non-treatment-seeking subjects with AUD (N=25) will be maintained on placebo and two doses of NAC (1.2 and 2.4 g/day). Two active doses will be tested in order to identify which dose is most effective and should be advanced to a clinical trial. Order of maintenance conditions will be randomly determined for each subject. After being maintained on each dose condition for 4 days, the reinforcing and subjective effects of ALC, including ALC craving, will be determined. Self-reported ALC use in the natural environment during maintenance will also be assessed. This reverse-engineered human laboratory approach has good predictive validity for clinical pharmacotherapy efficacy. After completing a session, subjects will undergo a 1-week washout and begin maintenance on the next condition, repeating this cycle until all conditions have been completed.

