4. STUDY POPULATION

Up to 150 individuals will be screened to participate in this study. We intend to enroll 25 (17 male and 8 female) completers into the study. Screening procedures will be conducted under our lab's screening protocol (03-0509). Inclusion and exclusion criteria are outlined below.

Inclusion/Exclusion Criteria

The following criteria must be met for an individual to participate in the study: 1) able to speak/read English; 2) not seeking treatment at the time of the study; 3) female or male between the ages of 21 and 55 years; 4) one binge drinking episode (5+/4+ standard alcoholic drinks per drinking session for men and women, respectively) in the past 30 days; 5) recent ALC use verified by ethyl glucuronide positive urine, as well as fulfillment of DSM-5 diagnostic criteria for AUD; 6) other than the diagnosis for AUD at the time of the interview, subjects must be otherwise healthy; 7) ECG, read by cardiologist, within normal limits; 8) body mass index of 19-35; 9) females using an effective form of birth control and not pregnant or breast feeding; 10) judged by the medical staff to be psychiatrically and physically healthy; 11) able to abstain from ALC for 12 hours prior to session; and 12) no contraindications/allergies to NAC or ALC. Potential research subjects who are seeking treatment for substance abuse/dependence will be excluded from research participation, and will be referred to an appropriate treatment program.

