Subjects will be instructed to maintain their standard diet, ALC and cigarette intake throughout participation, with the exception that they will be asked to abstain from ALC for at least 12h prior to a session. All subjects will provide urine and expired-breath samples prior to experimental sessions. The presence of drugs of abuse in the urine or positive BALs upon arrival for experimental sessions will result in rescheduling of the session. Repeated occurrences will result in study dismissal. Subjects will not be allowed to smoke tobacco cigarettes during experimental sessions, consistent with previous work (O’Malley et al., 2002).

NAC Maintenance Conditions. After completing screening, a subject will be randomized to a NAC dose order condition using a random number generator. Completing subjects will experience all dose conditions. A pharmacist in the Investigational Drug Service will maintain the randomization key to preserve the double blind. NAC doses will be prepared with commercially available drug placed into opaque capsules. Cornstarch will be used as filler. Placebo capsules will contain only cornstarch, but will be visually identical to capsules that contain NAC. Placebo capsules will also be washed in a NAC slurry to control for the

Behavioral Effects of Drugs: Inpatient (34) (Alcohol and N-Acetylcysteine) (PI: [name].)

distinct smell of NAC as has been done in previous research ([name]., Personal Communication). Subjects will receive practice taking the study capsules during the practice session. Subjects will be provided two placebo capsules during this session and instructed on how to correctly administer those capsules. Subjects will be told that these capsules are placebos, but that placebo and NAC capsules will look visually identical.

Total daily doses are 0, 1.2 and 2.4 g/day (i.e., 0, 0.6g and 1.2 g administered two times daily at 0700 and 1900h; Table 1). One of the doses reduced ALC use in one study (i.e., 1.2 g/day; Squeglia et al., 2016) and the other dose reduced elevated brain glutamate levels in another (i.e., 2.4 g/day; Schmaal et al., 2012). Testing two doses in this study will inform dose selection when NAC is advanced to a clinical trial. The dosing regimen and maintenance period were chosen based on previous studies (Amen et al., 2011; LaRowe et al., 2013; Squeglia et al., 2016).

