1975-2300h	Recreational activities (i.e., movies, magazines, and books).
2300h	Lights out.
0700h	Subject provided a standardized breakfast.
0730-0800h	BAL sample and field sobriety test.
0800h	Discharged from CSC and car keys returned.

Session Activities. On experimental session days, subjects will arrive at the LHBP at the University of Kentucky at 1400h. Upon arrival to the LHBP, the LHBP staff will take the subject's car keys and will return them when the subject is released from the hospital the following morning. Should the subject leave the hospital prior to that time, the LHBP staff or subject will arrange transportation (e.g., arrange a taxi). The car keys will be returned the morning following the experimental session upon successful completion of a field sobriety test.

Behavioral Effects of Drugs: Inpatient (34) (Alcohol and N-Acetylcysteine) (PI: [name].)

Urine and expired breath samples will be obtained for drug and ALC testing. A field sobriety test will be completed. Time of maintenance dosing will be confirmed by self-report and Wisepill® log. If subjects miss more than 3 doses or take doses more than 2 hours outside their scheduled window on 3 occasions within a single dose condition, they will be coached on adherence and that dose condition will be repeated. If this non-adherence occurs again during any other dose condition (or during the repeat condition), the subject will be dropped from the study. Subjects will report their ALC consumption during each 4-day maintenance block using the TLFB (Sobell et al., 1992). Subjects will be then admitted to the CSC at 1500h for their overnight stay and provided a light snack upon admission.

ALC Self-Administration Procedures. The reinforcing effects of ALC, alone and during maintenance on NAC will be assessed using a sophisticated clinical laboratory approach that has predictive validity for AUD pharmacotherapy efficacy (Drobes et al., 2003; Hendershot et al., 2016; O'Malley et al., 2002). The primary outcome measure for this procedure is Number of Drinks Chosen. Testing under this procedure involves two phases: 1) Sampling and 2) Self-Administration.

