Sampling Phase. Subjects will complete a Sampling Phase at 1600h during experimental sessions to acquaint them with ALC effects. During each Sampling Phase, subjects will receive a single administration of 95% ALC mixed with non-alcoholic mixer (e.g., lemon lime soda, tonic water) (designed to raise BALs to 0.03 g/dl), to be consumed over 5 minutes.

Self-Administration Phase. After sampling the ALC dose, subjects will complete the Self-Administration Phase. During each Self-Administration Phase, subjects will complete 2 1-h choice blocks in which they will be provided with a tray containing 4 drinks, with each drink prepared with 95% ALC mixed with non-alcoholic mixer (e.g., lemon lime soda, tonic water) (designed to raise BALs 0.015 g/dl/drink) and a “tab” detailing the cost of each drink, based on the cost of a drink purchased in a local bar (i.e., \$3.00). Subjects will be instructed to consume as many drinks on the tray as they want during the 1-h choice block. Subjects may instead choose to receive the corresponding dollar amount for the drinks that they do not consume. At the end of the first choice block, the drink tray will be replaced with a second tray of 4 drinks for the second choice block. Subjects can thus consume a maximum of 8 drinks or earn maximum of \$24, but may choose freely between these two options. Including money as an alternative reinforcer provides an incentive for not drinking ALC, which models the natural ecology. Any money earned will be added to that subject's \$40 payment for attending the session.

Subjective-Effects Questionnaires. Five standardized subjective-effects questionnaires that measure various aspects of mood and ALC effects (Ray et al., 2009; Roche et al., 2016) will be completed as outlined in Table 2: 1) ALC Urge Questionnaire to measure craving (Bohn et al., 1995); 2) Subjective High Assessment Scale (Schuckit, 1984); 3) Biphasic ALC Effects Scale (Martin et al., 1993); 4) Profile of Mood States (Schacham, 1983) and 5) Drug Effects Questionnaire (Johanson and Uhlenhuth, 1980).

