Data will be analyzed as raw scores. Statistical significance refers to $p < .05$. Number of Drinks Chosen on the ALC self-administration procedure will be analyzed with a one-factor, repeated-measure ANOVA with NAC dose (0, 1.2 and 2.4 g/day) as the factor. A significant attenuation (i.e., decreased ALC self-administration) will be inferred if the main effect of NAC attains statistical significance in the ANOVA. Tukey’s HSD *post-hoc* test will be used to make appropriate pair-wise comparisons between means if the ANOVA outcome attains statistical significance. Data from the subjective-effects questionnaires and safety/tolerability measures following administration of the sampling dose will be calculated as peak effect (i.e., the maximum score observed after ALC sampling). These data will be analyzed in the same fashion as ALC self-administration data. The influence of relevant biological (e.g., age) and behavioral variables (e.g., cigarette smoking, weekly ALC use) will be determined in initial correlation analyses and included as covariates in analyses should they be significantly associated with outcomes. Outcomes from trait questionnaires and cognitive behavioral tasks will also be correlated with self-administration, subjective effect and physiological data to explore the mechanisms by which NAC attenuates the effects of ALC.

Power and Sample Size Considerations. We used the results of a prior meta-analysis of human laboratory studies of ALC self-administration and craving to determine an appropriate sample size for the present experiment (Hendershot et al., 2016). That meta-analysis demonstrated that naltrexone maintenance decreased the quantity of ALC consumed and self-reported craving relative to placebo with an average estimated effect size (i.e., Cohen’s f) of approximately 0.27. Considering the overall design and use of three NAC doses, enrolling 25 subjects will provide sufficient power (power = 0.80, $\alpha = 0.05$, G*Power) to detect a medium effect size (f) of approximately 0.26 for attenuation of the effects of ALC as a function of NAC dose.

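### The three-period crossover is analysed with dose as the only factor and no stated balancing of dose orders; blocking the orders and adding a period term, as a pair, is a cheap gain in precision

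*Combined protocol and SAP*

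**What the plan says.** The primary test in Section 7 (Data Analysis) is a "one-factor, repeated-measure ANOVA with NAC dose (0, 1.2 and 2.4 g/day) as the factor". For the peak subjective and safety measures after the sampling drink, the plan adds: "These data will be analyzed in the same fashion as ALC self-administration data". No period, session or sequence term appears. The covariate rule in the same section gives only subject-level examples (age, smoking, weekly alcohol use).

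On order, Section 1 says "Order of maintenance conditions will be randomly determined for each subject", and Section 7 (NAC Maintenance Conditions) says "a subject will be randomized to a NAC dose order condition using a random number generator". Section 3 and Table 1 also say only that the order is random. Blocks, a Latin square or target counts per order are not mentioned, although a balanced list is not ruled out.

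Table 1 places the sessions on Days 5, 17 and 29. Section 4 gives the size: "We intend to enroll 25 (17 male and 8 female) completers into the study". Section 7 (Session Activities) says that after a set amount of non-adherence subjects stay in, but "they will be coached on adherence and that dose condition will be repeated". A second failure ends participation: "If this non-adherence occurs again during any other dose condition (or during the repeat condition), the subject will be dropped from the study".

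**The concern.** In a crossover, each subject's three results differ because of dose, because of noise, and because of anything that changes between the first and third visit. A dose-only model puts that last part into noise. Drift is plausible here: the Day 0 practice session gives no alcohol, so Session 1 is the first time a subject meets the study drinks and the choice between drinks and money.

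At stake are the power of the omnibus test and the width of the pairwise comparisons, which are meant to show which dose to take forward. If the list held by the pharmacist is in fact blocked, there is a different cost. Drift then inflates the error term without affecting the dose means, and the dose-only test becomes conservative.

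**Working it through.** **Inputs from the documents.** N = 25 completers, m = 3 doses, f = 0.26, alpha = 0.05, stated power 0.80. Three doses give 3! = 6 orders.

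**Assumptions, not stated in the documents.** Within-subject correlation r = 0.5, sphericity, total SD 1, evenly spaced dose means, drinks treated as continuous and normal (the real count runs from 0 to 8), and linear drift of d SD per period.

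**Step 1: reproduce the plan.** Noncentral F on 2 and 2 × 24 = 48 df, with lambda = N·m·f²/(1 − r) = 25 × 3 × 0.0676/0.5 = 10.14. Power is 0.795, matching the stated 0.80. Other values of r do not match: 0.4 gives 0.714 and 0.6 gives 0.880.

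**Step 2: add drift to the planned analysis, orders unblocked.** Period effects of +d, 0 and −d, randomly matched to dose, add 2d²/(3 − 1) = d² to the error variance. So lambda = 5.07/(0.5 + d²). The SE of the placebo minus 2.4 g/day contrast is √(2(0.5 + d²)/25).

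| d | lambda | power | SE (SD units) |
|---|---|---|---|
| 0 | 10.14 | 0.795 | 0.200 |
| 0.10 | 9.94 | 0.786 | 0.202 |
| 0.15 | 9.70 | 0.776 | 0.204 |
| 0.25 | 9.01 | 0.743 | 0.212 |
| 0.50 (extreme) | 6.76 | 0.610 | 0.245 |

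For an assumed SD of 2 to 3 drinks, d = 0.10 is 0.2 to 0.3 drinks per session and d = 0.25 is 0.5 to 0.75.

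**Step 3: the alternatives.** With perfect balance, a period term moves 2 df out of error (48 to 46) and leaves lambda at 10.14, giving power 0.794. The table below is from simulation, 40,000 trials per cell, Monte Carlo SE about 0.002.

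| Design and model | d = 0 | 0.10 | 0.15 | 0.25 |
|---|---|---|---|---|
| Unblocked, dose only (plan) | 0.796 | 0.786 | 0.774 | 0.740 |
| Unblocked, dose + period | 0.776 | 0.776 | 0.774 | 0.776 |
| Blocked, dose only | 0.799 | 0.790 | 0.781 | 0.748 |
| Blocked, dose + period | 0.796 | 0.796 | 0.795 | 0.796 |
| Blocked, dose + period, 30% removed at random | 0.788 | 0.792 | 0.790 | 0.790 |

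Under heavier disruption the pair gives:
- 50% removed at random: 0.781, 0.783 and 0.784 at d = 0, 0.10 and 0.25.
- 30% removed and 20% of subjects repeating a condition, period ranked 1 to 3: 0.782 to 0.788 at the same three drifts. Counting a repeat as a fourth session level gives 0.774 to 0.778.

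The removal and repeat rates are assumptions; the documents give none.

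**Step 4: compare with the plan's 0.795, 0.786 and 0.743.** With no drift the pair costs from nothing (0.796) to 1.4 points (0.795 − 0.781). At 0.10 it lies between 0.783 and 0.796 against 0.786, so break-even is near there. At 0.25 it gains 4 to 5 points (0.784 to 0.796 against 0.743).

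**Step 5: type I error (20,000 trials per cell).** Near 5% for unblocked dose-only at every drift, and 0.048 to 0.053 for the pair. Blocked dose-only falls to 0.045, 0.036 and 0.013 at d = 0.10, 0.25 and 0.50.

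**The case against.** The strongest reply is that nothing in the plan is wrong. Randomised order already protects the dose comparison, and a dose-only repeated-measures ANOVA is a valid test. A reader might infer biased dose effects or an inflated false-positive rate; Step 5 and the random order rule that out.

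The design also limits drift. Table 1 schedules a practice session matching the experimental one apart from alcohol and the overnight stay. Subjects are told to keep their usual diet, drinking and smoking. Testing is in individual rooms. The sampling drink, price and trays are the same at every session, and "Subjects will complete a Sampling Phase at 1600h during experimental sessions to acquaint them with ALC effects". These features make a large drift less likely. They do not exclude one, since Session 1 is still the first with alcohol. At 0.25 SD per period, the change from Session 1 to Session 3 would be 1.0 to 1.5 drinks for an SD of 2 to 3.

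A reader might also infer that the stated 0.80 is overstated, or that 28 completers are needed at 0.25 SD per period. That follows only if r = 0.5 excludes drift. Under random order, drift is already part of the observed correlation between dose conditions. If 0.5 is that observed correlation, the stated power is not eroded, and the period term adds to it: at d = 0.25, lambda = 5.07/(0.5 − 0.0625) = 11.59 on 2 and 46 df, giving about 0.85. The documents state neither r nor its basis, so no shortfall in sample size can be claimed.

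Finally, the list may already be balanced. That would supply half of the remedy, and it would strengthen the case for the period term.

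**Conclusion.** The point holds as a cheap improvement in precision. The plan names dose as its only factor and states no balancing of orders, so any drift across sessions goes into the error term. On the stated assumptions, planned power falls from 0.795 to 0.743 at 0.25 SD per period, while the pair stays at about 0.78 to 0.80.

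Neither half does the job alone. Blocking without a period term recovers almost nothing (0.748 at 0.25) and makes the test conservative. A period term without blocking costs about 2 points with no drift and pays off only above about 0.15 SD per period.

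The benefit depends on a drift that the documents do not quantify; below about 0.10 SD per period there is no gain. Drift was scaled only for drinking, so the size for the subjective and safety outcomes is not known.

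**What to change.** Make both changes together.

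1. State that the order list is generated in permuted blocks of the six dose orders. Balance will be approximate: 25 = 4 × 6 + 1, and removals disturb it among completers.
2. Analyse Number of Drinks Chosen, and the outcomes analysed the same way, with dose and period as fixed effects and subject as random. Base the Tukey comparisons on the period-adjusted dose means and that model's error term.

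State in advance that, where a condition is repeated, period is the chronological rank (1 to 3) of the sessions supplying the analysed data. This keeps three levels and 46 error df; a fourth level would cost about 1 further point of power.

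The cost is 2 error df, a blocked list, one sentence on coding, and about 0 to 1.4 points of power if there is no drift. If the orders cannot be blocked, the period term is optional.

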17. DATA AND SAFETY MONITORING

Data Monitoring Plan. Data will be collected using a computerized data collection and management system. This system automates the collection of the subjective-effect and physiological data, which ensures the accuracy and completeness of data collection. The data are stored in a unique file on the hard drive of the computer and are printed after all the tasks are completed. Paper-and-pencil task data are verified by staff and double-entered into excel spreadsheets after each session. In all instances, the data files do not contain the name of the subject; but instead, a unique four-digit number identifies each subject. A computer file linking the unique number with the subject's name will be kept on a stand-alone, password-protected computer. Data files for experimental tasks and physiological measures from each experimental session will be manipulated and combined into a single electronic spreadsheet for each subject by the PI. Data for all subjects will then be combined into a single electronic spreadsheet and separated by experimental measure for statistical analysis using SPSS (IBM Corporation, Armonk, NY).

The primary outcome for this study will be Number of Drinks during ALC self-administration. Secondary outcome measures will include craving, BALs, physiological and subjective response to ALC, self-reported ALC use in the natural environment during maintenance, as well as performance on cognitive-behavioral tasks, and the Udvalg for Kliniske Undersøgelser (UKU) Side Effects Rating Scale.

As noted above, the majority of data are collected using an automated computer system, which increases the accuracy and completeness of data collection and ensures the validity and integrity of the data. Hand written questionnaires and tasks are double-entered and verified by staff prior to analysis. The initial data manipulation described above will be conducted twice and compared. The quality of manipulated data and data analyses will be monitored by random inspection by the PI and/or Co-Investigators.

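### The primary rule infers reduced drinking from a significant three-level omnibus F alone and does not require any NAC dose to be shown below placebo

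*Combined protocol and SAP*

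**What the plan says.** Section 17 names the endpoint: "The primary outcome for this study will be Number of Drinks during ALC self-administration". Section 7, Data Analysis, analyses it with a one-factor repeated-measures ANOVA over 0, 1.2 and 2.4 g/day at the 5% level and gives the decision rule: "A significant attenuation (i.e., decreased ALC self-administration) will be inferred if the main effect of NAC attains statistical significance in the ANOVA". After a significant F, Tukey's HSD "test will be used to make appropriate pair-wise comparisons between means if the ANOVA outcome attains statistical significance". Placebo is not named in that sentence, although with three conditions Tukey's HSD covers both placebo pairs. Peak scores on the subjective-effects and safety measures are handled the same way.

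The aims are directional and dose-specific. Section 1 states: "The first aim is to demonstrate that maintenance on NAC reduces the pharmacodynamic effects of ALC that contribute to its abuse", and adds: "Two active doses will be tested in order to identify which dose is most effective and should be advanced to a clinical trial". Section 7, NAC Maintenance Conditions, repeats the second purpose: "Testing two doses in this study will inform dose selection when NAC is advanced to a clinical trial". No other section adds a direction or a placebo comparison to the decision rule.

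The power paragraph gives 0.80 power with 25 subjects for f of about 0.26, worded as power for attenuation.

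**The concern.** The hypothesis tested is not the conclusion drawn. The F test on 2 degrees of freedom asks whether the three means differ in any way; the rule concludes that NAC lowers drinking. A significant F can come from a dose above placebo, or from a difference between the two active doses when neither is distinguishable from placebo.

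At stake is the primary claim and the dose to carry into a clinical trial. A statement that NAC reduces self-administration, and a choice of dose, should each rest on a comparison with placebo. The plan has that comparison but does not tie the claim to it.

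**Working it through.** **Inputs from the plan (Section 7):** N=25, three conditions, alpha 0.05, f=0.26, stated power 0.80.
**Assumptions not in the documents:** within-subject correlation r=0.5 unless stated, sphericity, normal data with unit SD.

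**1. The plan's own figure.** The noncentrality is λ = f²·N·m/(1−r) = 0.0676 × 25 × 3/0.5 = 10.14, with 2 and 48 degrees of freedom and critical F = 3.191. Power is 0.795, which agrees with 0.80. With r = 0, 0.3 or 0.7 it would be 0.48, 0.64 or 0.96, so the stated figure corresponds to r=0.5.

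**2. A single data set that meets the rule.** Take means, in SD units from placebo, of 0, +0.3 (1.2 g/day) and −0.3 (2.4 g/day), with error variance 1 − 0.5 = 0.5. The variance of the means is 0.09, so F = 25 × 0.09/0.5 = 4.5 > 3.191. The Tukey critical difference is 3.420 × √(0.5/25) = 0.484. Each dose differs from placebo by 0.3, which is not significant; the two active doses differ by 0.6, which is. One NAC mean lies below placebo, so attenuation would be claimed even on a directional reading.

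**3. How often this happens.** Mean patterns were scaled to f=0.26. If one condition differs from the other two, the difference is d = 0.26 × 3/√2 = 0.5515 SD. If the effect is graded, each step is 0.26 × √(3/2) = 0.3184 SD. The simulation used 200,000 trials per pattern (standard error at most 0.11 points), pooled error on 48 df, and Tukey only after a significant F.

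| True pattern | F significant (literal rule) | F significant, some NAC mean below placebo (intended reading) | F significant, a dose Tukey-significantly below placebo |
|---|---|---|---|
| No effect | 5.0% | 3.3% | 1.6% |
| Only 2.4 g/day lowers drinking | 79.6% | 79.6% | 63.1% |
| Both doses lower it equally | 79.6% | 79.6% | 77.6% |
| Graded decrease | 79.5% | 79.5% | 77.3% |
| Both doses raise drinking | 79.4% | 0.1% | 0.0% |

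The 3.3% also follows directly: with no effect, placebo has the lowest of the three means in one third of trials whatever F is, and 5.0% × 2/3 = 3.3%.

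**4. What the gap consists of.** If only 2.4 g/day works, the gap is 79.6 − 63.1 = 16.5 points. In 13.8 of them only the two active doses differ significantly; in 1.9 no pair does; in 0.8 a dose is significantly above placebo and none below. Under no effect, the literal rule's 5.0 points split into 1.6 with a dose below placebo, 1.7 with a dose above it and none below, 1.2 with only the active pair significant and 0.5 with no significant pair (rounded).

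**5. Sensitivity.** For only 2.4 g/day working, significant F versus the Tukey condition is 48.2% vs 32.1% at r=0, 64.2% vs 46.7% at r=0.3, and 95.5% vs 86.9% at r=0.7. For both doses working it is 48.5% vs 46.0%, 64.0% vs 61.6% and 95.5% vs 94.7%.

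The outcome is a bounded count: "Subjects can thus consume a maximum of 8 drinks". Repeating the exercise with integers from 0 to 8 (assumed placebo means 2.7, 4.0 or 5.7; r about 0.5) gives 5.0–5.1% vs 1.6–1.7% under no effect, 78.8–79.4% vs 61.5–62.7% for one working dose, and 75.6–80.3% vs 73.4–78.3% for both. The picture does not change.

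**The case against.** The strongest reply is that the sentence is shorthand for a conventional sequence, an omnibus test followed by Tukey. The parenthesis and the aims make the direction plain, and the investigators will see the means and the pairwise results before they write anything. Much of this stands. A reader might infer that the plan would announce benefit when NAC raises drinking, with a chance of 79.4% in the last row of the table. That follows only from the literal wording; on the evident intention it is 0.1%.

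Three other strong readings also fail.
- The type I error of the F test is not inflated: 5.0% is its nominal level.
- The stated power of 0.80 is not a mistake; it is right for the omnibus test at r=0.5.
- Placebo comparisons are not missing, since Tukey's HSD includes them.

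It is also fair to say that the gap is large only if exactly one dose works, a pattern the documents do not specify, and that in that case the claim that NAC works is true. It has simply not been confirmed against placebo.

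What remains is that the intended direction does not supply a test. A NAC mean merely lying below placebo, next to a significant F, is weaker than a significant comparison with placebo, and the plan accepts the former as sufficient.

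**Conclusion.** The point holds as a fault in the stated decision rule, and it should be fixed. A significant F is the only written condition for inferring attenuation, and the Tukey comparisons that would support the claim have no role in it.

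That gap in the logic does not depend on any assumption. Its size does. With N=25, f=0.26, r=0.5, sphericity and normal data, and on the intended reading, the excess over a placebo-confirmed claim is about 1.7 points under no effect (3.3 − 1.6), about 2 points if both doses work or the effect is graded, and about 16.5 points if only one dose works. The last figure counts unconfirmed claims of a true effect, not false ones.

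**What to change.** 1. Replace the decision sentence in Section 7, Data Analysis, with:

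> Attenuation is inferred for a NAC dose only if the ANOVA main effect is significant and the Tukey HSD comparison of that dose with placebo is significant with a lower mean number of drinks. A significant F without this is reported as a difference among doses.

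2. Restate the power sentence. The 0.80 is the power of the omnibus F at r=0.5. Under the new rule the power to claim attenuation at f=0.26 is about 0.77 if both doses work or the effect is graded (repeated simulations gave 0.772 to 0.777), and about 0.63 if only one dose works. State r, sphericity and normality as assumptions.

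3. Apply the same condition, a significant Tukey comparison with placebo in a direction stated in advance, to the subjective-effects measures that share this analysis.

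The cost is a lower stated chance of a positive primary claim. Design, N, ANOVA and Tukey's HSD are unchanged, and pooled-error Tukey relies on sphericity just as the planned ANOVA does. Keeping the F test as a gate follows the plan. Tukey's HSD controls the familywise error without it, and the gate gives up only about 1.0 to 1.3 points when both doses work or the effect is graded.
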